14.1.3 Subject Follow-up

Every attempt should be made to follow the subject until the adverse event has resolved or until the Investigator determines the subject has returned to an acceptable state of health.

14.1.4 Reporting Serious Adverse Events (SAEs)

The Investigator must report **all serious adverse events within 24 hours**, irrespective of the relationship to study medication, to the CRO, by fax or by e-mail (as back-up option), completing the appropriate reporting form. The CRO will then forward this information to **EryDel** within one business day of receipt. The names of the CRO contact will be communicated to the investigators by the CRO prior to the start of subject enrollment.

The minimum information required for an initial report of a Serious AE is as follows:

- Sender of report (name, address of Investigator, site number),
- Subject identification (screening number),
- Protocol number,
- Reportable event.

All SAE reports and any case of overdose leading to an AE or SAE must be faxed using the appropriate reporting form to the following number within 24 hours:

PPD
[Redacted]
[Redacted]
[Redacted]
[Redacted]
[Redacted]
[Redacted]

In case of fax failure, all sites can use the following email address as back-up option:

PPD
[Redacted]

In case of death, a comprehensive narrative report of the case should be prepared by the Investigator and sent to the CRO by mail together with the Serious AE Form, retaining a copy on-site. If an autopsy is performed, a copy of the autopsy report should be actively sought by the Investigator and sent to the CRO as soon as available. A copy of the autopsy report will be retained on-site.

A follow-up Serious Adverse Event Report will be completed by the Investigator if important follow-up information (i.e., diagnosis, outcome, causality assessment, results of specific investigations) are made available after submission of the initial form. The follow-up form will be sent to the CRO as described above.

If the Investigator becomes aware of any deaths or Serious Adverse Events after the end of the 60-day follow-up window established in the protocol following investigational product administration, they will be reported to the CRO as described above.

14.2 Safety Reporting to Investigators, IRBs/IECs, and Regulatory Authorities

The Sponsor or their designee will be responsible for reporting all SAEs to regulatory authorities, investigators, and Independent Ethics Committees / Institutional Review Boards (IRBs/IECs), as applicable, in accordance with national regulations for the United States. For all active investigators located in the United States, the Sponsor or their designee will prepare an expedited report for all SAEs that are unexpected and potentially related to the study drug, and copies will be distributed according to all applicable laws and regulations. The investigational site also will forward a copy of all expedited reports to their IRB/IEC.

14.3 Reporting Overdose

If the investigational site staff administering the study medication reports that a subject was given more than the specified dose of study medication, this will be considered an overdose and must be reported immediately to the Investigator. Any instance of overdose, whether symptomatic or not, must be communicated to the CRO within 24 hours and be fully documented as a Serious Adverse Event. Details of any signs or symptoms and their management should be recorded including details of any antidote(s) administered.

14.4 Pregnancy

This study will exclude pregnant and breast-feeding patients, and females of childbearing potential, unless they are practicing adequate contraception, as determined by their Health Care Provider. As a further precaution, a serum pregnancy test will be performed at Screening and Baseline (Day 0), and repeated at

Version 1.0, 09May2015; Version 2.1, 16Nov2015; Version 3.0 (Amend. 1), 01Feb2016; Version 3.1 (Amend. 2), 28Apr2016; Version 3.2 (Amend. 3), 25May2016; Version 4.0 (Amend. 4), 29Nov2016; Version 5.0 (Amend. 5, Site-specific), 20Sep2017; Version 6.0 (Amend. 6), 29Sep2017; Version 7.1 (Amend. 7.1), Final 13 March 2018, Version 8.0 (Amend. 8.0), Final 23 April 2018; Version 10.0 (Amend. 10), Final 16 April 2019; Version 11.0 (Amend. 11), Final 24 Jun 2020

Months 6 and 12 (or at early discontinuation) for all young women who have had a menstrual period within the past year. Results of the pregnancy tests at Screening and Baseline must be negative for the patient to be randomized to treatment.

If a patient becomes pregnant during the study, she will be discontinued from the study immediately. Patients and their parents/caregivers should be instructed to notify the Investigator if it is determined that, after completion of the study they have become pregnant, either during the treatment phase of the study or within 30 days of completing the study. Whenever possible a pregnancy should be followed to term, any premature terminations reported, and the status of the mother and child should be reported to the CRO or EryDel after delivery.

Based on the estimated half-life of dexamethasone given with the EDS, i.e. less than 4 days, a period of one month of continued contraception should follow after study conclusion or early termination due to any reason.

14.5 Breaking the Study Blind by the Investigator

In case of emergency, the Investigator may break the blind for an individual patient, if the knowledge of the administered compound is deemed necessary for the safety of the patient. Breaking of the blind will be performed by the Investigator by calling/logging into the IVRS/IWRS system.

If the study blind is broken, the Investigator must immediately notify the CRO and provide the subject's number. The reason for breaking the blind should be noted on the Adverse Event (or Serious Adverse Event) section of the Case Report Form. EryDel will inform the Independent Safety Monitoring Board of the unblinding.

14.6 Independent Data Safety Monitoring Board

An independent Data Safety Monitoring Board (DSMB) will be established by EryDel to review the safety of all patients enrolled in this trial, on an ongoing basis. No EryDel employee or investigator involved in the EDS clinical studies will be a voting member of this board. The DSMB will regularly review the safety data as it accrues.

The Board will be regularly notified of the occurrence of any fatal or life threatening events immediately (within 7 calendar days) and any other serious adverse events within 15 calendar days. The Board will also receive updates on any adverse dropouts on a regular basis (once per month). The Board will have access to the blinded safety data including serious AEs and adverse dropouts, as well as clinically significant abnormal laboratory tests, vital signs and ECGs at periodic intervals. The Board may request an unblinding of the treatment groups if there is a safety concern.

The DSMB will review all of the safety data on an ongoing basis, with special emphasis on the incidence and severity of steroid related events, new infections, and serious AEs and deaths, in addition to the standard safety parameters. After reviewing the emerging safety profile for EDS-EP, the Board will make a recommendation to EryDel to (a) amend the ongoing study (e.g., increase safety monitoring, modify dosing), (b) terminate the EDS program (e.g., the EDS-EP safety profile is unacceptable), (c) continue the clinical program as designed. The current study protocol will not be amended or changed (this includes the study design and entry criteria) unless mandated by the emerging (unblinded) safety profile of EDS-EP.

Details of the DSMB charter (separate document) will be submitted to regulatory authorities, and will be available to IECs/IRBs upon request.

15 SUBJECT COMPLETION AND DISCONTINUATION

15.1 Definitions

A patient will be considered to have ‘completed’ the Initial Treatment Period of the study when he/she returns for the final evaluations on Month 6. ‘Discontinuation’ will refer to any subject who does not complete the full 6 months (± 30 days) of this initial post-baseline treatment period of the study. Patients who continue in the Extension Treatment Period will be considered to have ‘completed’ this period of the study when he/she returns for the final evaluations on Month 12. ‘Discontinuation’ will refer to any subject who does not complete the full 12 months (± 30 days) of this extension.

15.2 Procedures for Handling Withdrawals

In the absence of a medical contraindication or significant protocol violation, every effort should be made by the Investigator to keep the patient in the study; however, should the patient be withdrawn prior to Month 6 during the Initial Treatment Period or Month 12 during the Extension Treatment Period. All efforts should be made to complete all final evaluations and report the observations as thoroughly as possible at the time of the patient’s withdrawal, with an explanation of why the subject is withdrawing from the study.

The criteria for discharging a patient from the study prior to the final study examination are listed below. The Investigator must indicate the primary reason (only one can be reported) for discontinuation, as well as the date when the decision was made; these will be specified on the ‘End of Study’ form.

A patient may be withdrawn from study participation if:

- Any hypersensitivity or allergic reaction, clearly linked to the study medication, has occurred;
- the patient experiences an AE sufficiently severe, in the opinion of the investigator, that it contraindicates the patient continuing in the study;
If the patient experiences a systemic illness considered unrelated to the study medication, it still must be reported as an AE.
- the patient/caregiver withdraws consent (e.g. subject refuses to have any more blood samples taken for the EDS process; in this instance a specific reason must be recorded by the investigator);
- a major protocol deviation that jeopardizes the continued well-being of the patient or poses an risk to the patient’s health;
If the patient is able to abstain in the future from activities/behaviors that constituted a major protocol violation, the patient should be allowed to continue.
- the patient is lost to follow-up, i.e., the subject did not return to the clinic, and attempts to contact the subject were unsuccessful. Attempts to contact the subject must be documented;
- the Sponsor, IEC/IRB), or regulatory agency terminates the study.

Dropouts will not be replaced.

The Investigator may terminate a patient’s study participation at any time during the study if a patient meets the study termination criteria described above. In addition, a patient or his/her parent/guardian may discontinue the patient’s participation without giving a reason at any time during the study. Should a patient’s participation be discontinued, the primary reason for termination must be recorded. For patients who discontinue prior to Month 6/12, an attempt should be made to perform all final (Month 6/12) assessments on the patient, and to follow up on any safety issues until resolution. Patients who discontinue prematurely, but return for scheduled efficacy evaluations will become part of the RDO analysis population.

Version 1.0, 09May2015; Version 2.1, 16Nov2015; Version 3.0 (Amend. 1), 01Feb2016; Version 3.1 (Amend. 2), 28Apr2016; Version 3.2 (Amend. 3), 25May2016; Version 4.0 (Amend. 4), 29Nov2016; Version 5.0 (Amend. 5, Site-specific), 20Sep2017; Version 6.0 (Amend. 6), 29Sep2017; Version 7.1 (Amend. 7.1), Final 13 March 2018, Version 8.0 (Amend. 8.0), Final 23 April 2018; Version 10.0 (Amend. 10), Final 16 April 2019; Version 11.0 (Amend. 11), Final 24 Jun 2020

Patients who complete 12 months of treatment will be eligible for entry into the open-label study (Study IEDAT-03-2018), provided there are no issues that would preclude their continuing in the trial.

Patients who discontinue prematurely, as well as those patients completing the Initial Treatment Period (Month 6) and not continuing in the Extension Treatment Period, and those completing Month 12 of the study and not entering the optional open-label study (Study IEDAT-03-2018), should be followed up for 60 days after their final infusion regarding the occurrence of any Serious Adverse Events.

16 STATISTICAL METHODS

16.1 Analysis of Efficacy

Primary Efficacy Endpoint

The primary efficacy endpoint will be the change from baseline to the follow-up assessments at Days 90 and 180, in the total score on the ‘Modified’ International Cooperative Ataxia Rating Scale (ICARS).

Key Secondary Efficacy Endpoint

The key secondary efficacy end point is the CGI-C rating of change from baseline at the follow-up assessments at Days 90 and 180.

Other Secondary Efficacy Endpoints

The following secondary efficacy endpoints will be assessed in the study:

- The change of CGI-S score from baseline to follow-up based on repeated measures at Days 90 and 180
- The change of VABS score from baseline to follow-up based on repeated measures at Days 90 and 180

Tertiary Efficacy Endpoints

The following tertiary efficacy endpoint will be assessed in the study:

- The change of QOL scores (EQ-5D-5L scale) from baseline to follow-up based on repeated measures at Days 90 and 180.

This measure will be considered exploratory.

16.2 Statistical Methods

All data collected on the A-T NEST from the selected centers on Day 2 and subsequent visits will be delivered to John Hopkins Statistical group for evaluation of the data, and performance of any analyses needed to determine/ confirm the psychometric properties of the scale.

16.2.1 Sample Size

Based on the very low prevalence of AT, as well as the high disability, morbidity and mortality, the number of subjects available for prospective trials is extremely limited. Furthermore, only aggregate Phase II study results are available ([IEDAT-ERY01-2010 Clinical Study Report](#)). Hence, in the absence of a file with the raw item score for each subject, the treatment effect and variability of the ‘Modified’ ICARS is unknown. Therefore the parameters needed to identify an appropriate sample size for this study were estimated using the aggregate Phase II results.

Sample size calculations are based on the analysis of the primary efficacy variable (i.e., ‘Modified’ ICARS) under the following assumptions.

- For aggregate ICARS, a treatment difference of 3.7 - 4.2 for the ~14-22 mg dose versus placebo with respect to ICARS measurements is expected, with a standard deviation of 5.0 - 7.4 ([IEDAT-ERY01-2010 Clinical Study Report](#)).

Version 1.0, 09May2015; Version 2.1, 16Nov2015; Version 3.0 (Amend. 1), 01Feb2016; Version 3.1 (Amend. 2), 28Apr2016; Version 3.2 (Amend. 3), 25May2016; Version 4.0 (Amend. 4), 29Nov2016; Version 5.0 (Amend. 5, Site-specific), 20Sep2017; Version 6.0 (Amend. 6), 29Sep2017; Version 7.1 (Amend. 7.1), Final 13 March 2018, Version 8.0 (Amend. 8.0), Final 23 April 2018; Version 10.0 (Amend. 10), Final 16 April 2019; Version 11.0 (Amend. 11), Final 24 Jun 2020

- For ‘Modified’ ICARS, the treatment difference is expected to be less than the aggregate ICARS, therefore, instead of examining a treatment difference between 3.7 and 4.2, the range between 3.0 and 3.7 was examined. The decrease in treatment difference is expected given that most of the questions in the Kinetic Function domain are not included in the ‘Modified’ ICARS and [Chessa et al \(2014\)](#) reported this domain as demonstrating the greatest overall improvement.
- For ‘Modified’ ICARS, the standard deviation is expected to be more than the aggregate ICARS, therefore, instead of examining a standard deviation between 5.0 and 7.4, the range between 5.0 and 8.0 was examined. This increase is expected given that removing questions from health assessment instruments can decrease precision and increase standard deviations ([Awad, 2008](#); [McHorney et al, 1992](#); [McHorney, 1997](#)).
- The primary efficacy variable will be tested, comparing ~14-22 mg dose versus placebo at the 0.05 two-sided significance level. Testing of the ~5-10 mg dose versus placebo will only proceed if the ~14-22 mg dose is significant. Consequently, no adjustment for multiplicity is needed for testing the two dose levels.

Table 4 below provides power estimates for the range of potential treatment differences and standard deviations. Estimates must be based on ranges, since point value estimates for ‘Modified’ ICARS are not available.

Table 4. Power given treatment difference and standard deviation estimates for a sample size of 54

Treatment Difference	Standard Deviation	Power
3.0	5.0	99.3%
	6.0	95.7%
	7.0	88.3%
	8.0	78.7%
3.2	5.0	99.7%
	6.0	97.5%
	7.0	91.9%
	8.0	83.6%
3.4	5.0	99.9%
	6.0	98.6%
	7.0	94.6%
	8.0	87.8%
3.6	5.0	>99.9%
	6.0	99.3%
	7.0	96.6%
	8.0	91.1%
3.7	5.0	>99.9%
	6.0	99.5%
	7.0	97.3%
	8.0	92.5%

As seen in Table 4, a sample size of 54 provides sufficient power for a study design with two repeated measures to assess the primary efficacy endpoint of change from baseline in ‘Modified’ ICARS between two groups with a two-sided 0.05 significance level, when the treatment difference ranges between 3.0 and 3.7, and the standard deviation ranges between 5.0 and 7.0 (PASS®, Module “Tests for Two Means in a Repeated Measures Design”).

Version 1.0, 09May2015; Version 2.1, 16Nov2015; Version 3.0 (Amend. 1), 01Feb2016; Version 3.1 (Amend. 2), 28Apr2016; Version 3.2 (Amend. 3), 25May2016; Version 4.0 (Amend. 4), 29Nov2016; Version 5.0 (Amend. 5, Site-specific), 20Sep2017; Version 6.0 (Amend. 6), 29Sep2017; Version 7.1 (Amend. 7.1), Final 13 March 2018, Version 8.0 (Amend. 8.0), Final 23 April 2018; Version 10.0 (Amend. 10), Final 16 April 2019; Version 11.0 (Amend. 11), Final 24 Jun 2020

The final sample size will be adjusted for 10% loss to follow-up, for a final sample size of about 60 per group. It is anticipated that the screen failure rate will be approximately 25%; therefore, at least 240 patients would need to be screened to enroll 180 eligible patients. Due to the Covid-19 outbreak, the enrollment was closed with 175 randomized patients as of the 30th of March 2020. Statistical guidance determined that 175 patients (versus the goal of 180 patients) would not materially change the power of the study.

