3.1 Efficacy Endpoints

Initial 6-Month Treatment Period

Primary Efficacy Endpoint

- The change of the Modified International Cooperative Ataxia Rating Scale (mICARS) scores from baseline to Visit 9. The change in the full ICARS from baseline to Visit 9 will be presented as a sensitivity analysis.

Key Secondary Efficacy Endpoint

- CGI-C at Visit 9

Other Secondary Efficacy Endpoints

- The change of CGI-S (structured) score from baseline to Visit 9.
- The change of VABS score from baseline to follow-up based on repeated measures at Visit 6 and Visit 9

Tertiary Efficacy Endpoints

- The change of QOL scores (EQ-5D-5L scale) from baseline to follow-up based on repeated measures at Visit 6 (“Month 3”) and Visit 9 (“Month 6”)

Supplemental Analysis

The modified ICARS will be rescored, using two separate methods, collapsing categories within specific items. Each method will result in a smaller total sum score across the ICARS domains. These will be referred to as Rescored mICARS Method 1 (key opinion leader [KOL] suggested) and Rescored mICARS Method 2 (CCI definition), to prevent confusion with modified ICARS. Details of the mapping to each of these abbreviated scales are presented in [Appendix II](#) and [Appendix III](#), respectively, of this document.

Extension Treatment Period (Months 6 to Month 12 of the study)

For the Extension Treatment Period, comparisons will be made for the ‘Modified’ ICARS, CGI-C, CGI-S (structured), VABS, and QoL [EQ-5D-5L] using the same methods as for the initial treatment period with missing values imputed in the same way. In addition, the full ICARS, Rescored mICARS Method 1, and Rescored mICARS Method 2 will be evaluated using the same methods as the modified ICARS.

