Table 3. Power given treatment effect and standard deviation estimates for a sample size of 54

Treatment Effect	Standard Deviation	Power
3.0	5.0	99.3%
	6.0	95.7%
	7.0	88.3%
	8.0	78.7%
3.2	5.0	99.7%
	6.0	97.5%
	7.0	91.9%
	8.0	83.6%
3.4	5.0	99.9%
	6.0	98.6%
	7.0	94.6%
	8.0	87.8%
3.6	5.0	>99.9%
	6.0	99.3%
	7.0	96.6%
	8.0	91.1%
3.7	5.0	>99.9%
	6.0	99.5%
	7.0	97.3%
	8.0	92.5%

[figure not shown]
As seen in the above table, a sample size of 54 provides sufficient power for a study design with two repeated measures to assess the primary efficacy endpoint of change from baseline in ‘Modified’ ICARS between two groups with a two-sided 0.05 significance level, when the treatment effect ranges between 3.0 and 3.7, and the standard deviation ranges between 5.0 and 7.0 (PASS®, Module “Tests for Two Means in a Repeated Measures Design”).

The final sample size was adjusted for 10% loss to follow-up, for a final sample size of about 60 per group. It was anticipated that the screen failure rate would be approximately 25%; therefore, at least 240 subjects would need to be screened to enroll 180 eligible subjects.

Sample size was based on the primary efficacy parameter from the Version 10.0, Final, 16 April 2019 IEDAT-02-2015 protocol, the ‘Modified’ ICARS. The computed sample size is sufficient to maintain at least 80% power for the full ICARS, given the range of treatment differences and range of standard deviations available for the full ICARS from the IEDAT-ERY01-2010 Clinical Study Report described above and the powers computed for the selected ranges of treatment effect and standard deviation for the ‘Modified’ ICARS.

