5.3.1 Primary Efficacy Variable

The modified ICARS total score from the central rater (with speech domain scores from local raters) at baseline and each follow-up visit, and the change and percent change from baseline to each follow-up visit, will be summarized using descriptive summary statistics by treatment group.

The primary efficacy variable, change from baseline to follow-up (Visit 6 [“Month 3”] and Visit 9 [“Month 6”]) in mICARS total score (described above), will be analyzed using a mixed model repeated measures (MMRM) analysis, with the baseline mICARS value as covariate and five fixed effects (treatment, age [6 to <10 years, ≥ 10 years], sex, region, visit) and one interaction term (treatment-by-visit). The treatment effect, together with the associated two-sided 95% CI and p-value will be calculated. Unstructured covariance matrices will be used. Model effect estimation will be based on restricted maximum likelihood (REML). The region-by-treatment interaction can be tested in a separate model and if a significant interaction is found, then a forest plot will be used to present the region-specific treatment effects and associated 95% confidence intervals.

The primary MMRM analysis will assume missing at random (MAR) as a means of handling missing data.

Sensitivity analyses of these primary analyses will consist of ANCOVA at Visit 9 (‘‘Month 6’’) with missing data imputed using multiple imputations as described in [Section 5.1.3](#), LOCF, and OC. The results from each of the sensitivity analyses will be compared to the primary MMRM analysis.

When applying the multiple imputation methods describe in [Section 5.1.3](#), the regression method will be used, and the imputation model will be the same as the analysis model, based on the factors treatment, sex, age (category), region, and baseline mICARS; the pattern of missing data will be essentially monotonic since none of the factors used in the model are expected to be missing. One hundred iterations of the model will be run, and the results will be combined with SAS PROC MIANALYZE. For Multiple Imputation Method #2, multiple imputation based on subjects taking the same treatment will be applied first to the missing data due to COVID-19 related restrictions, and then Jump to Reference will be applied to the remaining missing data.

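### The power table matches uncorrelated Month 3 and Month 6 scores averaged together; its 88.3% (3.0 points, SD 7) is about 60% for the SAP's Visit 9 endpoint

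*Protocol*

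**What the plan says.** Protocol 16.2.1 sizes the trial for the mICARS, "comparing ~14-22 mg dose versus placebo at the 0.05 two-sided significance level". For the treatment difference "the range between 3.0 and 3.7 was examined", and for the standard deviation "the range between 5.0 and 8.0 was examined". Table 4 gives power for 54 patients per group, and the text concludes that "a sample size of 54 provides sufficient power for a study design with two repeated measures to assess the primary efficacy endpoint" when the SD lies between 5.0 and 7.0. It names a PASS module for two means in a repeated measures design. SAP 5.1.7 repeats the table as Table 3 and adds: "The computed sample size is sufficient to maintain at least 80% power for the full ICARS". Neither document gives a within-patient correlation or a covariance pattern for the calculation.

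The endpoint is described in two ways.

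- SAP 3.1: "The change of the Modified International Cooperative Ataxia Rating Scale (mICARS) scores from baseline to Visit 9", a single visit. Protocol 7.3 and 12.1.1 also place it at Month 6, and Protocol 16.2.8 has the primary analysis compare the groups after six months.
- Protocol 16.1, and likewise 16.2.7: "the change from baseline to the follow-up assessments at Days 90 and 180", two visits.

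SAP 5.3.1 fits both visits in an MMRM with a treatment-by-visit term and then says: "The treatment effect, together with the associated two-sided 95% CI and p-value will be calculated". It does not say whether that effect is the Visit 9 contrast or the average over both visits.

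**The concern.** A second measurement on the same patient adds information to a two-visit average only to the extent that it is not correlated with the first. It adds almost nothing to a comparison made at one visit. A power table that credits the second visit as a fresh, independent patient overstates power on either reading of the endpoint, and most of all on the SAP's reading.

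Two things are at stake. First, the claim of sufficient power for SD 5 to 7, and the later reassurance that 175 patients instead of 180 makes no material difference, both rest on this table. A non-significant result would be read as stronger evidence against an effect than the design can give. Second, the Visit 9 difference and the two-visit average are different tests with different power. Unless one is named before unblinding, the confirmatory test is not fully specified.

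**Working it through.** **Inputs.** Two-sided alpha 0.05; 54 per group; differences 3.0 to 3.7; SD 5.0 to 8.0; two follow-up measures (all Protocol 16.2.1). Phase II baseline SD of the full ICARS, 12.8 (Protocol 7.1.3.1). The correlation rho between the two change scores is not stated.

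**Formula.** For the mean of two visits, power = Phi(delta / [SD × sqrt((2/54) × (1 + rho)/2)] − 1.96). For one visit, the factor (1 + rho)/2 becomes 1. Note sqrt(2/54) = 0.19245.

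**Step 1: reproduce the plan's figure.** At 3.0/SD 7 with rho = 0: 3.0 / (7 × 0.19245 × 0.7071) = 3.149; 3.149 − 1.96 = 1.189; Phi = 88.3%, as printed. The same assumption reproduces all 20 cells to the printed decimal. With rho = 0.1 the worst cell is already 3.9 percentage points off.

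**Step 2: what rho could be.** If raw scores have a common variance s² and a common correlation r at baseline, Month 3 and Month 6, each change has variance 2s²(1 − r). The covariance of the two changes is s²(1 − r), because both subtract the same baseline. So rho = 0.5 whatever r is.

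**Step 3: two-visit mean, 3.0/SD 7.**

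| rho | Power |
|---|---|
| 0 (matches the table) | 88.3% |
| 0.3 | 78.9% |
| 0.5 | 73.0% |
| 0.7 | 67.6% |
| 0.9 | 62.7% |

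**Step 4: Visit 9 alone.** At 3.0/SD 7: 3.0 / (7 × 0.19245) = 2.227; 2.227 − 1.96 = 0.267; Phi = 60.5%. The noncentral t gives about 60% as well. Each cell shows stated power, then Visit 9 power:

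| Difference | SD 5 | SD 6 | SD 7 | SD 8 |
|---|---|---|---|---|
| 3.0 | 99.3 / 87.7 | 95.7 / 73.8 | 88.3 / 60.5 | 78.7 / 49.5 |
| 3.2 | 99.7 / 91.4 | 97.5 / 79.1 | 91.9 / 66.1 | 83.6 / 54.7 |
| 3.4 | 99.9 / 94.2 | 98.6 / 83.8 | 94.6 / 71.4 | 87.8 / 59.8 |
| 3.6 | >99.9 / 96.3 | 99.3 / 87.7 | 96.6 / 76.2 | 91.1 / 64.7 |
| 3.7 | >99.9 / 97.0 | 99.5 / 89.3 | 97.3 / 78.4 | 92.5 / 67.1 |

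No SD 7 cell reaches 80%. With 175 randomized and 10% loss, 175/3 × 0.9 = 52.5 per arm, and 3.0/SD 7 gives 59.3%.

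**Step 5: full ICARS.** At 3.7/SD 7.4, inside the range the SAP cites: 3.7 / (7.4 × 0.19245) = 2.598; 2.598 − 1.96 = 0.638; Phi = 73.8% for Visit 9, below the claimed 80%.

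**Step 6: can baseline adjustment recover it?** Take 7.4 as the SD of change, 12.8 as the baseline SD, and an equal SD at follow-up (assumptions). The correlation of baseline with change is then −7.4 / (2 × 12.8) = −0.289, and the adjusted SD is 7.4 × sqrt(1 − 0.289²) = 7.1. More generally, covariates correlating 0.3 or 0.5 with change raise the 60.5% to 64.6% or 73.0%. Getting back to 88.3% needs a correlation of 0.707.

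**The case against.** The zero correlation is inferred, not stated. The same factor of 1/sqrt(2) would arise from a single-visit ANCOVA whose covariates correlate 0.707 with change, or from raw-score SDs with a baseline correlation of 0.75, since sqrt(2 × 0.25) = sqrt(0.5). That is true, so the table does not prove rho = 0. But neither alternative is described anywhere, the named method is a repeated-measures one, and a raw-score SD of 5.0 to 7.4 sits badly with a Phase II baseline SD of 12.8.

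The 60.5% is for an unadjusted comparison, whereas the MMRM adjusts for baseline, age, sex and region. That stands as a caveat: the planned power will be somewhat higher. Step 6 rests on the full ICARS in 22 open-label patients, and the mICARS is a different, 54-point scale, so the gain cannot be fixed exactly.

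The shortfall is also not uniform, and this stands too. In the SD 5 to 7 range, 8 of 15 cells reach 80% for Visit 9 (all five at SD 5, three at SD 6). For the two-visit mean at rho 0.5, 13 of 15 do. On that reading the full-ICARS corner of 3.7/SD 7.4 gives 89.7%, 85.1% and 80.5% at rho 0.3, 0.5 and 0.7, so the SAP's sentence fails only on the Visit 9 reading.

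Finally, enrolment is closed, and restating power changes no estimate or type I error. That is so for the table. It does not answer the unnamed contrast, even though most passages point to Month 6.

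**Conclusion.** The concern holds. The printed power fits an average of two uncorrelated visits, an assumption that neither document states and that a shared baseline makes untenable. For the endpoint in SAP 3.1, 54 per arm gives 60.5% at 3.0/SD 7 against 88.3% stated, 73.8% against 95.7% at SD 6, and 49.5% against 78.7% at SD 8. The claim of sufficient power fails throughout SD 7 and for 3.0 and 3.2 points at SD 6; it survives at SD 5. On the reading kinder to the plan, the two-visit mean, 3.0/SD 7 gives 67.6% to 78.9% for rho from 0.7 down to 0.3. For scale, 80% power at Visit 9 for 3.0/SD 7 would need about 86 per arm.

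These figures take the stated SD as the SD of change and assume no covariate gain. A covariate correlation of about 0.71 with change would be needed to restore 88.3%, and neither document claims one.

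**What to change.** 1. In Protocol 16.1 and 16.2.7 and in SAP 3.1 and 5.3.1, name one primary test: the Visit 9 LS-mean difference in mICARS change, high dose versus placebo, from the MMRM. Do this before the initial-period blind is broken.
2. Restate Protocol Table 4 and SAP Table 3 for that contrast. Alternatively, state the assumed within-patient correlation and covariance pattern and show power for rho from 0.3 to 0.7. State that the SD is of change, and give any covariate gain as an explicit assumption.
3. Reword the conclusion of sufficient power so that it covers only the differences and SDs for which it holds.
4. Restate or withdraw the SAP 5.1.7 sentence on the full ICARS; at 3.7/SD 7.4 the Visit 9 figure is 73.8%.

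The cost is protocol and SAP wording and a less favourable stated power. No added patients or assessments are needed, and the fitted model does not change.
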